10. STATISTICAL ANALYSES

10.1. Randomization, Stratification, and Masking

Eligible subjects will be randomly assigned to each of treatment groups in a 1:1 ratio according to a validated SAS® computer-generated central randomization schedule. The randomization schedule contains the coded treatment assignments for each randomization number. The

randomization plan will be based on the study design, number of treatment groups and number of sites.

The randomization is generated by an un-masked statistician who is not affiliated with the study. The randomization plan is shared with the Sponsor's designee responsible for final clinical packaging and labeling to allow for proper packaging and labeling of the study drug supply. Access to the randomization code will be strictly controlled according to the Sponsor designee's Standard Operating Procedures (SOPs).

The randomization is not unmasked until the study is complete and the database is locked. The Sponsor will confirm in writing that there are no regulatory or quality issues which preclude the unmasking of the study.

Unmasking of the randomization code prior to study completion due to a medical emergency will be managed in accordance with the Sponsor designee's SOP. All unmasked cases will be fully documented. Otherwise, the study mask will remain intact.

In this double-masked study, the investigator and his/her study staff, the subject (including caregiver, if applicable) and Sponsor/designee (other than as stated above) are masked to the identity of the study drug.

10.2. Efficacy and Safety Variables

Primary Efficacy Endpoint(s): The primary efficacy endpoint will be the proportion of subjects with ACC grade of 0 (cell count=0) at Day 15. Subjects with an ACC grade of >0 at Day 15 or who receive rescue medication prior to Day 15 will be treated as failures. Last-observation-carried-forward (LOCF) will be used for the intent-to-treat (ITT) analysis.

Secondary Efficacy Endpoint: The secondary efficacy endpoint is the proportion of subjects who achieve a pain score of 0 at each post-surgical VAS (0-100 millimeter [mm] scale) assessment (Days 1, 8, 15, 22 and 32).

Safety Variables: AEs, BCVA, IOP, biomicroscopic and ophthalmoscopic findings.

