7. CONCOMITANT MEDICATIONS

Disallowed medications include:

- Any corticosteroid at least 15 days before surgery and throughout the duration of the study;
- Depot-corticosteroids in either eye at least 45 days before surgery and throughout the duration of the study;
- Administration of any nonsteroidal anti-inflammatory drugs (NSAIDs) including but not limited to topical, systemic (including sleep-aids containing NSAIDs), inhaled, or irrigation solution at least 1 week before surgery and throughout the duration of the study, with the exception of aspirin, where oral doses of 165 mg/day or lower are allowed;
- Ocular or systemic antihistamines (including sleep-aids containing an antihistamine), or mast cell stabilizers in either eye at least 1 week before surgery and throughout the study's dosing period;
- Triamcinolone in either eye at least 90 days before surgery and throughout the study's dosing period;
- Medications used to treat benign prostatic hyperplasia throughout the duration of the study;
- Inhaled, ingested, sublingual, transdermal or topical products containing marijuana, tetrahydrocannabinol (THC) or cannabidiol (CBD) at least 1 week before surgery and throughout the study's dosing period and for one day after the study's dosing period ends;
- Systemic pain relievers, analgesics (e.g., pregabalin, gabapentin, opioids) 14 days before surgery and throughout the duration of the study;
- Any supplement, prescribed medication or over-the-counter product that the investigator feels may interfere with the study parameters, including homeopathic remedies, analgesics, and pain medication.

During the study dosing period (Day -1 through Day 14), if the investigator determines that a rescue medication is necessary due to lack of efficacy (whether at a planned study visit or at an unscheduled visit), the subject should be discontinued from the study drug and the appropriate rescue medication prescribed. The subject should continue to be seen for all remaining study visits to assess safety and efficacy. This information must be recorded in the subject's source record and on the appropriate eCRF.

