10.3. Analysis Populations

Safety Population: The safety population includes all randomized subjects who receive at least 1 dose of the study drug. Subjects in the safety population will be analyzed in the treatment group for the study drug they received.

Intent-to-Treat Population: The Intent-to-Treat (ITT) population will include all randomized subjects who undergo routine uncomplicated unilateral cataract surgery. Subjects in the ITT population will be analyzed in the treatment group to which they were assigned by the randomization scheme, regardless of which study drug they receive.

Per Protocol Population: The per-protocol (PP) population will include all subjects in the ITT population who have no major protocol deviations during the study.

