10.6. Efficacy

10.6.1. Primary Efficacy Analysis

The primary efficacy analysis will test for a difference in the proportion of subjects with ACC grade zero (0) in the SURF-201 active treatment group versus the vehicle group only at Day 15. An ACC grade of zero is considered to be a success, and an ACC grade >0 or the use of rescue medication prior to Day 15 is counted as a failure (as described in Section 3.1). Missing data will be imputed using LOCF in the ITT population only.

The test will be the z-test for proportions and will be reported with associated z-based 95% confidence interval (CI). The null hypothesis is that the proportions are equal, and this will be a two-sided test at the alpha = 5% level. If the assumptions of the z-test are not satisfied, a Barnard's exact test and exact 95% CIs will be presented.

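### Rescue use is the only drug use that overrides an ACC grade of 0, so a disallowed anti-inflammatory given for another recorded reason before Day 15 can still be scored as a success

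*Combined protocol and SAP*

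**What the plan says.** Section 10.2 makes the primary endpoint the proportion of subjects with ACC grade 0 at Day 15. It names two routes to failure: a grade above 0 at that visit, or being among those "who receive rescue medication prior to Day 15 will be treated as failures". Section 10.6.1 repeats the rule: grade 0 is a success, and "the use of rescue medication prior to Day 15 is counted as a failure".

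Rescue is described in one place only. The last paragraph of Section 7 says what happens "if the investigator determines that a rescue medication is necessary due to lack of efficacy": study drug is stopped, rescue is prescribed and follow-up continues. There is no list of rescue drugs and no definition for scoring.

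The same section disallows, as separate items, "Any corticosteroid at least 15 days before surgery and throughout the duration of the study" and "Administration of any nonsteroidal anti-inflammatory drugs (NSAIDs) including but not limited to topical" and other routes, with low-dose oral aspirin excepted. It attaches no endpoint consequence to either.

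Under Section 10.3 the ITT "population will include all randomized subjects who undergo routine uncomplicated unilateral cataract surgery". The per-protocol (PP) set removes ITT subjects with major protocol deviations, a term the plan does not define.

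**The concern.** Section 7 disallows these drugs for the length of the study, so the plan itself treats them as able to disturb the outcome. Yet exposure counts against a subject only if it is called rescue. Suppose two subjects receive the same anti-inflammatory in the study eye on the same day and both have ACC grade 0 at Day 15. If one record says lack of efficacy and the other says adverse event, the first is a failure and the second a success.

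The label has some play in it. Under Section 9, worsening of cells, flare, injection and similar signs need not be recorded as an adverse event unless the investigator judges it appropriate, so the same clinical picture can be filed either way.

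If such use occurs in the vehicle arm, extra successes dilute the treatment difference. In the active arm they inflate it.

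**Working it through.** The plan states no power, assumed response rates or expected use of disallowed drugs, so there is no figure to reproduce. The check is a trace through the text, followed by an illustration of sensitivity.

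**Trace.** Take a subject who has surgery, receives a disallowed corticosteroid or NSAID on, say, Day 8 for a recorded adverse event, and has ACC grade 0 at Day 15.

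1. Population (10.3): the subject was randomized and had surgery, so is in ITT.
2. Missing data (10.4): LOCF fills missing observations. Day 15 is observed, so LOCF does not apply.
3. Grade (10.2, 10.6.1): the grade is 0, so the first failure route does not apply.
4. Rescue (10.2, 10.6.1, 7): the drug was not given for lack of efficacy, so on the only description available it is not rescue, and the second route does not apply.
5. Score: success for the assigned arm.

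Change only the recorded reason to lack of efficacy, and step 4 makes the subject a failure. Section 10.6.1 refers the failure rule to a Section 3.1, but Section 3 (Study Conduct) has no numbered subsections in the text available, so the cross-reference does not settle the matter.

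**Size.** Inputs from the plan: 40 subjects per arm (Section 2) and a two-sided z-test for proportions at 5% (10.6.1). Assumptions: all 40 per arm reach surgery, the pooled form of the z-test is used, and the success counts are invented for illustration.

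- One subject moves an arm's rate by 1/40 = 2.5 percentage points.
- z = (p1 − p2) / √[p̄(1 − p̄)(2/40)], where p̄ is the pooled proportion.
- Reported 20/40 v 10/40: p̄ = 30/80 = 0.375; z = 0.25/√(0.375 × 0.625 × 0.05) = 2.31; p = 0.021.

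The table rescores subjects from that reported result.

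| Rescored as failures | Counts | Difference (points) | z | p |
|---|---|---|---|---|
| None | 20 v 10 | 25.0 | 2.31 | 0.021 |
| One in each arm | 19 v 9 | 25.0 | 2.34 | 0.019 |
| Two in each arm | 18 v 8 | 25.0 | 2.39 | 0.017 |
| One, active arm only | 19 v 10 | 22.5 | 2.09 | 0.036 |
| Two, active arm only | 18 v 10 | 20.0 | 1.88 | 0.061 |
| Two, vehicle arm only | 20 v 8 | 30.0 | 2.81 | 0.005 |

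Balanced rescoring leaves the result almost where it was. Only imbalance between arms matters, and with 40 per arm an imbalance of two can cross the 5% line from this starting point.

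**The case against.** **Section 7 is a conduct instruction, not a definition.** It says what to do when rescue is needed for lack of efficacy, and 10.2 and 10.6.1 use the word without repeating that limit. A data reviewer could read rescue more broadly. This stands as a caution: the narrow meaning is the only one described, not one the plan imposes. But it leaves an undefined term deciding the primary outcome.

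**The per-protocol set deals with these subjects.** Taking a disallowed drug is an obvious candidate for a major deviation, so it would be wrong to infer that nothing in the plan could touch them. Even so, "major" is undefined, and excluding a subject from PP does not alter the ITT score.

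**Most ocular use would be rescue anyway.** A steroid given for worsening inflammation would ordinarily be for lack of efficacy. This narrows the gap without closing it, because Section 9 leaves adverse-event labelling of such signs to judgement.

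**Keeping the observed outcome is a legitimate ITT choice.** It is, under a treatment-policy approach. But the plan has already chosen composite failure for rescue. Applying one approach or the other to the same drugs according to the recorded reason needs to be stated if it is intended.

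**Causation and balance.** A reader might infer that the eye was cleared by the other drug, or that the primary result is likely to be reversed. The documents support neither. A subject with grade 0 may have cleared regardless, and nothing suggests that incidental use in a masked trial would gather in one arm. The one-arm rows in the table show sensitivity, not expected bias.

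**Conclusion.** The concern holds as a gap in how the endpoint is scored. As written, rescue is the only drug use that overrides grade 0, and other use of a disallowed anti-inflammatory before the Day 15 reading has no stated consequence. The ITT primary outcome can therefore turn on the recorded reason rather than on exposure.

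The size cannot be estimated, because the plan gives no frequency for such use. What can be said is that each affected subject is worth 2.5 points in one arm, that balanced use changes little, and that only an imbalance would matter. This rests on 40 analysed per arm and on assumed success counts. It does not establish that any observed clearance would be due to another drug, nor that the trial's conclusion is at risk. The gap is worth closing before unmasking because the trial is small and the change is cheap.

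The calendar wording of the cut-off (before Day 15, rather than before the Day 15 reading) is minor, and the same edit resolves it.

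**What to change.** In Sections 10.2 and 10.6.1, score as a failure any subject who, after surgery and before the Day 15 ACC assessment, receives any of the following, whatever the recorded reason:

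- rescue medication;
- an ocular corticosteroid or NSAID disallowed by Section 7, in the study eye;
- a systemic corticosteroid.

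Identify these subjects from the concomitant-medication eCRF before unmasking. The start at surgery matters: without it, use during the pre-surgical washout periods in Section 7 would make a subject a primary failure.

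Pre-specify two sensitivity analyses: one that also counts incidental systemic NSAID use as failure, and one under the current rule. A single systemic NSAID dose is a real trade-off and should not decide the main result by itself. Correct the reference to Section 3.1 in the same edit.

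The cost is a change of wording and one derivation from data that Section 8 already has documented at each visit. The downside is that a few subjects whose eye would have cleared anyway will be scored as failures. The change affects outcome scoring only, not what any patient receives.

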10.3. Analysis Populations

Safety Population: The safety population includes all randomized subjects who receive at least 1 dose of the study drug. Subjects in the safety population will be analyzed in the treatment group for the study drug they received.

Intent-to-Treat Population: The Intent-to-Treat (ITT) population will include all randomized subjects who undergo routine uncomplicated unilateral cataract surgery. Subjects in the ITT population will be analyzed in the treatment group to which they were assigned by the randomization scheme, regardless of which study drug they receive.

Per Protocol Population: The per-protocol (PP) population will include all subjects in the ITT population who have no major protocol deviations during the study.

10.4. Data Handling: Handling of Missing Data

The primary efficacy analysis for the ITT population will use the LOCF method to impute missing observations due to COVID-19 or otherwise [EMA. Guideline on Missing Data in Confirmatory Clinical Trials [Internet]. 2010. Available from: <https://www.ema.europa.eu/en/missing-data- confirmatory-clinical-trials>].

Partial dates and missing dates will not be imputed. Any classifications based on partial or missing dates will assume a “worse case” scenario. If a medication cannot be classified as either prior or concomitant due to missing or partial start and stop dates, it will be considered to be concomitant. If an AE cannot be classified as resolved prior to the end of the study period due to missing or partial stop dates, it will be assumed to be ongoing.

10.5. Statistical Methods: General Principles

All data processing, summarization and analyses will be performed using Sponsor designee’s SAS Environment / Version 9.4 (or later) of the SAS® statistical software package. The principles that will be applied to all tables, listings and figures (TLFs) unless otherwise stated are outlined in Table 1.

Table 1: Principles for All TLFs

Principle	Value
Baseline	Defined as the last measurement taken prior to dosing (Day -14 to Day -2).
Significant tests	Two-sided and use a 5% significance level for main effects and 10% significance level for interaction terms.
Treatment group labels and order presented	SURF-201 Vehicle
Tables	Data in summary tables presented by treatment group, assessment and visit (where applicable).
Listings	All data collected presented by treatment group, site, subject number, and visit (where applicable), unless otherwise specified.
Descriptive summary statistics for continuous variables	Number of subjects/observations (N), mean, standard deviation (SD), median, minimum (min) and maximum (max).
Descriptive summary statistics for categorical variables	Frequency counts and percentages [n (%)]
Denominator for percentages	Number of subjects in the analysis population, unless stated otherwise
Include “Missing” as category	No, N will change, unless stated otherwise
Display for 0 percentages	-
Display to one more decimal place than collected value	Mean Standard Error Mean Difference Median
Display to two more decimal places than collected value	Standard Deviation Confidence Interval
Date Format	DD-MMM-YYYY

10.6. Efficacy

10.6.1. Primary Efficacy Analysis

The primary efficacy analysis will test for a difference in the proportion of subjects with ACC grade zero (0) in the SURF-201 active treatment group versus the vehicle group only at Day 15. An ACC grade of zero is considered to be a success, and an ACC grade >0 or the use of rescue medication prior to Day 15 is counted as a failure (as described in Section 3.1). Missing data will be imputed using LOCF in the ITT population only.

The test will be the z-test for proportions and will be reported with associated z-based 95% confidence interval (CI). The null hypothesis is that the proportions are equal, and this will be a two-sided test at the alpha = 5% level. If the assumptions of the z-test are not satisfied, a Barnard's exact test and exact 95% CIs will be presented.

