4.2. Exclusion Criteria

The following are exclusion criteria for prospective study subjects to be confirmed from Day -14 – Day -2 (at Visit 1) prior to randomization:

1. Subject has any intraocular inflammation (cells and flare in the anterior chamber) or ocular pain (pain score of >0) in either eye prior to surgery.
2. Subject has any extraocular inflammation in the study eye prior to surgery (blepharitis is allowed if only scurf is present without any concurrent conjunctivitis or lid erythema/edema) or ongoing uveitis.
3. Subject has a history of diabetic retinopathy and/or previous vitrectomy in the study eye within the last 2 years prior to Screening which, in the investigator's opinion, is clinically significant and could impact the normal outcome of an uncomplicated cataract surgery.
4. Subject has a diagnosis of severe dry eye in the study eye.
5. Subject has any sign of iritis or scleritis in the study eye.
6. Subject has a history of glaucoma surgery in the study eye within the last 2 years prior to Screening.
7. Subject has a history of retinal surgery in the study eye within the last 2 years or plans to undergo retinal surgery in the study eye during the study period (from Screening through Day 32)

8. Subject has a history of Fuchs' dystrophy in the study eye.
9. Subject has guttata or chalazion in the study eye.
10. Subject has undergone radial keratotomy, photorefractive keratotomy, advanced surface ablation, corneal transplant, or LASIK in the study eye within the last 2 years prior to Screening.
11. Subject plans to undergo cataract surgery in the non-study (fellow) eye during the study period (from Screening through Day 32).
12. Subject plans to undergo additional ocular surgery (including femtosecond laser-assisted cataract surgery, minimally invasive glaucoma surgery, astigmatic keratotomy, limbal relaxing incision surgery, mechanical pupillary expanders, conjunctival incisions, and vitrectomy) in either eye during the study period (from Screening through Day 32).
13. Subject has a history of intraocular injections in the study eye within 6 months prior to Screening.
14. Subject has a history of herpes simplex infection in either eye.

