8. CLINICAL ASSESSMENTS/EXAMINATION PROCEDURES

The ophthalmic examinations listed below will be conducted in the surgery eye (study eye) and in the order specified. The fellow eye (non-study eye) may be examined at the investigators' discretion.

Subject Assessment of Pain via Diary: Surgery eye (study eye) pain will be evaluated prior to each study drug dose using a pain scale included in the dosing and pain assessment diary that subjects complete at home.

Investigator Assessments include the following:

Visual Analog Scale (VAS) (ocular symptoms): Eye pain/discomfort will be evaluated at Screening Visit 1 (Day -14 to Day -2) and at Visit 3 through Visit 7 (Day 1 through Day 32) using a VAS, scoring from 0 to 100 using a mark on a 100 mm line (0 = absent; 100 = maximum).

Best-Corrected Visual Acuity (BCVA): BCVA will be measured at Screening Visit 1 (Day -14 to Day-2) and at Visit 3 through Visit 7 (Day 1 through Day 32) (log of the minimum angle of resolution [logMAR] score using ETDRS [Early Treatment Diabetic Retinopathy Study] chart will be used to measure BCVA). A pinhole test may be performed at Visit 3 (Day 1).

Biomicroscopy: Slit lamp biomicroscopy, including the evaluation of anterior chamber cell (ACC) and anterior chamber flare, chemosis, bulbar conjunctival injection, ciliary injection, corneal edema, and keratic precipitates will be conducted by a board-certified ophthalmologist at Screening Visit 1 (Day -14 to Day -2) and at Visit 3 through Visit 7 (Day 1 through Day 32).

Ophthalmoscopy: Ophthalmoscopy will be performed at Screening Visit 1 (Day -14 to Day-2) and Visit 5 (Day 15) by a board-certified ophthalmologist. Ophthalmoscopy will be performed at Visit 7/Early Discontinuation Visit only if not performed at Visit 5.

Intraocular Pressure (IOP): IOP will be measured at Screening Visit 1 (Day -14 to Day-2) and at Visit 3 through Visit 7 (Day 1 through Day 32) in mmHg using a Goldmann applanation tonometer.

Standard examinations for subjects undergoing cataract surgery will be conducted by the investigator or qualified designated staff. However, ophthalmoscopy and biomicroscopy examinations will be performed by the same board-certified ophthalmologist who performs a subject's cataract surgery. All ratings and procedures should be performed by the same examiner from visit to visit whenever possible.

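### As written, LOCF for the primary endpoint can carry forward the pre-surgical ACC grade of 0, so an operated subject with no ACC exam through Day 15 and no rescue counts as a success

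*Combined protocol and SAP*

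**What the plan says.** Three sections set the imputation rule for the primary ITT analysis.

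- Section 10.2: "Last-observation-carried-forward (LOCF) will be used for the intent-to-treat (ITT) analysis".
- Section 10.4: the primary ITT analysis "will use the LOCF method to impute missing observations due to COVID-19 or otherwise".
- Section 10.6.1: "Missing data will be imputed using LOCF in the ITT population only".

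None says which observations may be carried, or how to count a subject with nothing post-surgical to carry. Success is grade 0. Failure is a grade above 0 at Day 15 or rescue before Day 15; a missing grade is not listed as a failure.

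Four other places decide what the last observation can be.

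- Section 10.3: the ITT population "will include all randomized subjects who undergo routine uncomplicated unilateral cataract surgery". No post-operative assessment is required.
- Section 8: biomicroscopy, which includes the ACC grade, "will be conducted by a board-certified ophthalmologist at Screening Visit 1 (Day -14 to Day -2) and at Visit 3 through Visit 7". Visit 3 is Day 1, so surgery on Day 0 falls between the first and second scheduled grades.
- Section 4.2, criterion 1, excludes a subject on this ground: "Subject has any intraocular inflammation (cells and flare in the anterior chamber").
- Section 10.5, Table 1, gives the baseline as "Defined as the last measurement taken prior to dosing (Day -14 to Day -2"), so the Screening grade is a recorded measurement in the data.

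**The concern.** Where baseline is the diseased state, carrying it forward is usually conservative. Here baseline comes before the surgery that causes the inflammation, and eligibility fixes it at the best possible grade. Carrying it to Day 15 therefore gives the best outcome to a subject about whom nothing is known after surgery, and does so in the primary analysis. The bias favours whichever arm has more such subjects, so its direction cannot be known in advance. By section 10.6.1, imputation applies in the ITT population only. A per-protocol analysis would presumably not use the carried value, but that does not correct the primary result.

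**Working it through.** **Tracing the rule**

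1. The subject is randomized and has routine uncomplicated surgery, so is in the ITT population (10.3).
2. There is no ACC exam on Day 1, 8 or 15, and no rescue is recorded.
3. The last ACC grade on file is from Screening (8), and it is 0 in effect (4.2, criterion 1).
4. LOCF fills Day 15 with 0 (10.2, 10.4, 10.6.1).
5. Grade 0 is a success (10.2, 10.6.1).

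No provision interrupts this chain.

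**How often it could arise**

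The documents keep the case narrow. One Day 1 or Day 8 exam supplies a post-surgical grade. Rescue before Day 15 is a failure whatever LOCF gives. Section 7 keeps rescued subjects in follow-up. Section 8 names an early discontinuation visit: "Ophthalmoscopy will be performed at Visit 7/Early Discontinuation Visit only if not performed at Visit 5". What remains is mainly a subject lost right after surgery.

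**Size**

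From the plan: 40 per arm, two-sided 5% z-test for two proportions. The plan gives no response or loss rates, so every rate and count below is an assumption. The plan also states no figure to reproduce.

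Test statistic, with pooled proportion p̄ = (a + b)/80:

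z = (a/40 − b/40) / √[p̄(1 − p̄)(1/40 + 1/40)]

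One subject moves an arm by 1/40 = 2.5 points. A borderline example:

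- 17/40 v 8/40: p̄ = 25/80 = 0.3125, z = 0.225/0.1036 = 2.17, p = 0.030.
- 16/40 v 8/40: p̄ = 24/80 = 0.30, z = 0.200/0.1025 = 1.95, p = 0.051.

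For average behaviour, let r be the proportion of an arm with no post-surgical exam and p its true success rate. The analysed rate is p(1 − r) + r if these subjects are scored as successes and p(1 − r) if scored as failures. For example, p = 0.50 and r = 0.025 give 0.5125 and 0.4875. Summing exact binomial probabilities over all outcomes with p < 0.05 gives the chance of rejection:

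| Assumed true rates | Assumed loss | Scored success | Scored failure | Nothing missing |
|---|---|---|---|---|
| 50% v 25% | 2.5% in both arms | 62.2% | 62.7% | 64.7% |
| 50% v 25% | 2.5%, active only | 69.0% | 60.3% | 64.7% |
| 50% v 25% | 2.5%, vehicle only | 57.7% | 67.0% | 64.7% |
| 15% v 15% | 2.5% in both arms | 5.2% | 5.4% | 5.3% |
| 25% v 25% | 2.5% in both arms | 4.9% | 5.0% | 5.0% |
| 15% v 15% | 2.5%, active only | 6.0% | 5.4% | 5.3% |
| 25% v 25% | 2.5%, active only | 5.4% | 5.1% | 5.0% |
| 15% v 15% | 5%, active only | 8.1% | 5.5% | 5.3% |
| 25% v 25% | 5%, active only | 6.6% | 5.2% | 5.0% |

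A loss of 2.5% is about 1 of 40 and 5% is about 2 of 40.

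If exactly one subject has no exam (39 observed in that arm, 40 in the other), the chance that success and failure coding give different 5% verdicts is:

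- 8.6% at true 50% v 25% if the subject is on active treatment, and 9.3% if on vehicle;
- 3.8% at equal true rates of 15%, and 3.0% at equal true rates of 25%.

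**The case against.** The strongest reply is that the fault is read out of silence. The plan never says that a Screening grade may be carried. Table 1 treats baseline as a separate item, the endpoint is tied to Day 15, and many programmers would carry only post-baseline values. That makes the literal reading less likely, but the documents do not state that convention. If it is intended, the plan still does not say whether a subject with no post-surgical grade is a failure or is left out.

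Table 1 offers a second reading: missing is not a category and N changes, so such a subject might drop out of the denominator. That is a general display rule with an exception for anything stated otherwise, and LOCF is stated. It also sits badly with the same table's default denominator, the whole analysis population.

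Third, criterion 1 speaks of cells and flare together, and a subject enrolled in error would stay in ITT, so a Screening grade of 0 is not strictly guaranteed. Its lead words cover any intraocular inflammation, so 0 remains the natural reading.

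What stands fully is the rarity and the weakness of the one-sided scenarios. Equal loss causes no inflation of the error rate in these calculations. The 8.1% figure needs about 2 of 40 active subjects unexamined and none on vehicle, which nothing in the documents suggests. The verdict-change probabilities apply only if such a subject exists.

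**Conclusion.** The concern holds, as a minor point. Followed literally, the stated rule scores as a success an operated ITT subject who has no ACC exam through Day 15 and no recorded rescue, and nothing in the documents prevents it. The expected effect is small: with equal 2.5% loss, power at assumed rates of 50% v 25% changes by about half a point between codings. The exposure lies in a close result, where a single subject can decide significance. The conclusion about the rule rests on the text alone. All figures for its size rest on assumed response and loss rates with 40 per arm.

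**What to change.** In sections 10.2, 10.4 and 10.6.1 (or once in 10.4, with cross-references from the other two), add: *Only post-surgical ACC grades up to Day 15 may be carried forward. ITT subjects with none are counted as failures and stay in the denominator.* LOCF can remain the primary method. Settle the wording before unmasking, so that the coding is not chosen with results in view.

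A count of imputed subjects by arm would show whether the rule was ever used. A sensitivity analysis that counts every missing Day 15 grade as failure is an optional, low-cost addition.

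The cost is a short clause and, if adopted, one by-arm count; no new visits, data or subjects are needed. Observed success rates may be slightly lower. Failure scoring is one choice among several, though it matches how the plan treats rescue. It is not free of bias when losses differ by arm: in the table above, 2.5% active-only loss at 50% v 25% takes power from 64.7% to 60.3%. At an equal true rate of 50%, 5% active-only loss gives 6.3% rejection under either coding, against 5.7% with nothing missing.
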